### 3.2 Endpoints

In order to assess implementation and effectiveness of the cardiovascular CPR (targeted at GPs) on the management of chest pain and patient's outcome, we will measure:

- Hospitalizations, severe CHD at 9 months among patients included
- Number and type of extra investigations and referrals run by GPs to manage patient's chest pain
- Use/non use of the CPR by GPs, acceptability and satisfaction

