### 3.5 Data collected in the CRF

A case report form (CRF) has to be filled in by all the GPs for each patient included to define patient's characteristics, current pain, personal history of cardiovascular disease and risk factors. It will also provide investigators with information regarding complementary investigations, referrals or hospitalizations for each patient at the time of index visit.

GPs of the intervention group will be asked to calculate the risk of cardiogenic chest pain for each patient with the CPR. The CRF also includes questions directly addressed to GPs to appreciate use, satisfaction and acceptability of the CPR.

GPs who belong to the usual care group will have to evaluate the risk of cardiogenic chest pain according to their clinical judgement only.

As all the items of the CPR are part of usual practice (patient's history and physical examination) investigators will be able to calculate patients' risk of cardiogenic chest pain a posteriori in the usual care group with the data collected in the CRF.

[figure not shown]
(See Annex 2 for complete CRF)

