#### 4.4 Selection and recruitment procedure

Swiss GPs and physicians of the Department of Ambulatory Care and Community Medicine in Lausanne will be contacted and asked to participate the study. Starting from a defined date, each GP will enrol a defined number of patients reporting any type of chest pain, according to inclusion criteria.

Sampling of all the GPs recruited will be performed in order to assess characteristics of participants (age, place, type of practice) and minimize cohort effect. Investigators may decide to use pre-existing GPs network such as Sentinella, which can insure correct sampling of Swiss GPs.

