## 6. Evaluation criteria

Aiming to assess both implementation of the cardiovascular CPR and its potential effect on chest pain management, evaluation criteria are split in two classes. On one hand, criteria concerning use of the CPR, evaluated by few questions in de CRF directly addressed to GPs. On the other hand, criteria aiming to measure impact of the CPR on chest pain management and patient's outcome. These are to be filled in by GPs for each patient complaining of chest pain at the time of the index visit (CRF) and at the end of follow-up (6 to 9 months), and by research team for intermediate analysis.

Implementation:	
Acceptability of the CPR	
 
- Use/non use of the CPR
 
- Reassurance with low-risk result
 

Satisfaction	
 
- Discrete visual analogue scale
 

Impact:	
Extra investigations of chest pain	
 
- None
 
- ECG
 
- Thoracic radiography
 
- Laboratory (CRP, FSC, CK, D-dimers, Troponines, BNP)
 
- Cardiac stress test
 
- Others (precise)
 

Referral	
 
- None
 
- Hospital / emergency setting
 
- Cardiologist (less than 6 hours, less than one week, more than one week, telephonic interview)
 
- New consultation
 
- Other (precise)
 

Patient's outcome at 9 months	
 
- Hospitalisation(s) during follow-up
 
- CHD / no CHD, with degree of certainty (discrete visual analogue scale)
 

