## 10.2 Data analysis

- a) Sampling and characteristics of GPs recruited (+/- Baseline Survey)
- b) Patients characteristics in usual practice group versus CPR group (age, sex, personal history of cardiovascular disease, cardiovascular risk factors, emergency consultation, telephonic interview, home visit, chest pain as main or secondary complaint)
- c) Patients characteristics within CPR group: low-risk versus high-risk of cardiogenic chest pain

- d) Impact of the CPR within CPR group

	CPR < 5 points (low risk)	CPR 5 to 7 points (intermediate risk)	CPR > 7 points (high risk)
Extra investigations			
Referral			
Patient's outcome			

- e) CPR calculated *a posteriori* in usual practice group, endpoints values and comparison of endpoints in low risk patients of usual practice group versus CPR group
- f) CPR group versus usual practice group

	CPR	Usual practice
Extra investigations		
Referral		
Patient's outcome		

- g) Implementation: use/non use rate of the CPR, acceptability and satisfaction.

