**Impression diagnostique :**

Suspicion maladie coronarienne : oui  / non

Degré de certitude : faible 0 – 1 – 2 – 3 – 4 fort

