**Examens en urgence (effectués au moment de la consultation) :**

Aucune  ECG  Radiographie thorax  Test d'effort

Laboratoire: FSC  CRP  Troponines  CK   
BNP  D-dimères

Autre(s)  (préciser) : \_\_\_\_\_

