**Suite de prise en charge :**

Aucune  Hôpital/Urgences

Consultation par cardiologue : délai <6 heures  <1 semaine  >1 semaine   
avis téléphonique

Consultation de contrôle au cabinet

Autre(s)  (préciser) : \_\_\_\_\_

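### The 9-month CHD / no CHD comparison says little about CHD not recognised at the index visit, and no listed analysis links the GP's index suspicion to the retained diagnosis

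*Protocol*

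**What the plan says.** Objective 2 (section 2) is to spare investigations without compromising management or outcome. Section 6 sets the patient outcomes at 9 months as hospitalisation during follow-up and "CHD / no CHD, with degree of certainty (discrete visual analogue scale". Section 3.2 words the endpoint differently: "Hospitalizations, severe CHD at 9 months among patients included". The end-of-follow-up form (Annex 3) records only CHD yes or no with a 0–4 certainty score and has no severity field.

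Section 10.2 uses patient outcome in three places: by score category within the CPR group (d), as a "comparison of endpoints in low risk patients of usual practice group versus CPR group" (e), and by arm (f).

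The index form (Annex 2) asks "Suspicion maladie coronarienne", yes or no with certainty. The item is not restricted to the CPR group, unlike the score and score-appraisal blocks. Both arms also record same-visit tests, under "Examens en urgence (effectués au moment de la consultation", and onward management, including hospital or emergency referral and "Consultation par cardiologue : délai <6 heures". Section 3.5 confirms that the form covers "complementary investigations, referrals or hospitalizations for each patient at the time of index visit". None of analyses a) to g) crosses index suspicion with the diagnosis retained at follow-up.

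**The concern.** The specific risk of a rule-out tool is that a patient with CHD is set aside at the first visit. Total CHD at 9 months does not register that event. Delayed recognition leaves the total unchanged, and permanent non-recognition lowers it. Similar totals, or a lower total in the CPR arm, could be read as support for the safety half of objective 2 when they are compatible with more missed CHD.

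Analysis e) does not remove the problem. Within low-score patients, total CHD mainly reflects the score's own false negatives, whatever the GP concluded. The information needed to do better is already collected in both arms; it is simply not used.

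**Working it through.** **Plan's own figures.** Section 10.1 gives 150 GPs per arm with 50 patients each: 150 × 50 = 7,500 per arm and 15,000 in total, as stated. The coefficient of variation (CV) between GPs is 0.2. The sample size is not in dispute.

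**Inputs from the protocol.** CHD prevalence is 12% (section 1.1), so 0.12 × 7,500 = 900 CHD patients per arm. Sensitivity of unaided GPs is 82.9%, against 90.0% when aided (section 1.2, Marburg score, difference not significant).

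**Assumptions.** Underlying CHD is equal in the two arms. Randomisation supports this only if enrolment does not differ: the CPR group is trained before the trial (Annex 1), and "each GP will enrol a defined number of patients reporting any type of chest pain" (section 4.4). Index sensitivity s is taken as 82.9% in usual care and 77.9% with the CPR; the 5-point fall is mine, for illustration. The share d of unsuspected CHD that is diagnosed by 9 months is unknown, so a range is shown.

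**Formulas.**
- Total CHD = 0.12 × [s + (1 − s) × d]
- CHD retained but not suspected at index = 0.12 × (1 − s) × d
- 95% half-width = 1.96 × √{sum over arms of [p(1 − p)/(150 × 50) + CV² × p²/150]}
- Power = Φ(difference/SE − 1.96)

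CHD patients not suspected at index: 900 × 0.171 = 154 in usual care and 900 × 0.221 = 199 with the CPR.

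Each cell gives usual care v CPR, then the difference in percentage points, then half-widths at CV 0.2 / 0.5 / 1.0.

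| d, both arms | Total CHD | CHD not suspected at index |
|---|---|---|
| 100% | 12.00% v 12.00%; 0 (1.17 / 1.71 / 2.91) | 2.05% v 2.65%; 0.60 (0.50 / 0.55 / 0.72) |
| 75% | 11.49% v 11.34%; −0.15 (1.14 / 1.64 / 2.78) | 1.54% v 1.99%; 0.45 (0.43 / 0.47 / 0.58) |
| 50% | 10.97% v 10.67%; −0.30 (1.11 / 1.58 / 2.64) | 1.03% v 1.33%; 0.30 (0.35 / 0.37 / 0.44) |

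Total CHD shows either no difference or a small one in the CPR arm's favour, far inside its interval. The linked outcome has the right sign throughout but limited precision. Its power is 66% (d = 100%, CV 0.2), 47% (75%, CV 0.5) and 39% (50%, CV 0.2). The fall in sensitivity detectable with 80% power is 6.0 points (d = 100%, CV 0.2) or 7.7 points (75%, CV 0.5). With 10% loss (45 patients per GP) and CV 0.2, the half-widths become 0.52 at d = 100% and 0.45 at d = 75%.

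**Unequal work-up.** If d is 100% in usual care but 75% with the CPR, the linked outcome is 2.05% v 1.99%, a difference of −0.06 (half-width 0.46 at CV 0.2), so the harm is hidden. The sign reverses once the CPR arm's d falls below 0.171/0.221 = 77% of usual care's.

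**Opposite direction.** With 90.0% sensitivity in the CPR arm and d = 100%, the linked outcome is 2.05% v 1.20%, a difference of −0.85 (0.41 / 0.45 / 0.56). Total CHD is again 12.00% in both arms, so a real benefit would be missed too.

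**Low-score stratum, 10.2 e).** At the validation sensitivity of 85.6%, 0.12 × 0.144 × 7,500 ≈ 130 CHD patients per arm score below 5. The same number is expected in both arms whatever the GP suspected.

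**The case against.** The strongest reply is that safety does not rest on total CHD alone. Hospitalisation is listed first among the outcomes, was one of three sizing variables, and is limited to chest pain on the follow-up form. Later consultations, tests and specialist visits are also recorded. This stands in part: these items carry some of the safety question and must be kept. They are indirect, because hospitalisation for chest pain does not show whether CHD had been recognised at index. A reader might infer that the trial has no safety measure; the protocol does not support that.

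A second reply is that the analysis plan could add a cross-tabulation. It could, but the protocol itself chooses this outcome and lists the analyses that use it.

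A third is that no suspicion is not the same as a missed case. This stands. Annex 1 says the CPR is not a decision rule and requires investigation when score and impression conflict. A patient marked no whose same-visit ECG reveals CHD has not been failed, so a stricter version is needed beside the simple one. The 3-month form also should not be pooled in, since a research nurse completes it by telephone for agreeing patients only.

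A fourth is that the independent review links initial diagnosis to later condition. It does, in 20% of cases (3,000 of 15,000), but as quality control and not as an arm comparison.

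Finally, the linked outcome still depends on CHD being diagnosed, and the CPR is meant to reduce work-up. This also stands and limits what the outcome can show.

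**Conclusion.** The concern holds as a weakness in the chosen outcome and the listed analyses. Total CHD at 9 months is largely insensitive to CHD not recognised at the index visit and, where some of it is never diagnosed, tilts towards the arm that misses more. In the illustration, a 5-point fall in index sensitivity moves total CHD by 0 to −0.30 points, against 0.30 to 0.60 points for the linked outcome when later ascertainment is equal.

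This rests on comparable enrolment, 12% prevalence, and sensitivities and later-diagnosis shares that the protocol does not establish for the Swiss score. Two stronger readings are not supported. A reader might infer that the CPR will cause more missed CHD; the only comparison quoted, 90.0% against 82.9%, points the other way, though for the Marburg score and without significance. A reader might also infer that the linked outcome would settle safety. It would not: its power for the assumed gap is about 66% at best, and unequal work-up can hide the effect entirely. The change is worth making, as a supportive outcome.

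**What to change.** Add to section 6 and 10.2 f) a supportive safety outcome: CHD retained on the 9-month end-of-follow-up form in a patient marked no for suspected CHD on the index form. Report a stricter version with equal prominence, which also requires no ECG, stress test or cardiac laboratory test and no hospital or cardiologist referral at index. Compare both by allocated arm over all enrolled patients, with a cluster-adjusted risk difference and 95% confidence interval. Report the converse as well: suspected at index, no CHD retained.

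Read these with chest-pain hospitalisation, total CHD and later investigations and referrals, not in their place. State in the protocol that neither similar total CHD nor a null result on the new outcome is by itself evidence of safety, because the unblinded GP makes the diagnosis and lower work-up in the CPR arm can mask missed CHD.

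The cost is a derived variable (with its stricter version) and an added comparison, with no new data collection. The downside is limited power. The stricter version will have fewer events still; how many fewer cannot be calculated from the protocol.

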## 7. Data collection and management

### 7.1 Source data

- CRF filled in by GPs for each patient included at index visit (see Annex 2, in French)
- Intermediate analysis questionnaire (see Annex 3, in French)
- End of follow up questionnaire (see Annex 3, in French)

### 7.2 Documents storage and keeping

The documents collected during the current study are the CRF, questionnaires filled in by research team at 3 months and end of follow up questionnaires for each patient included. All the files regarding the current trial will be kept at the Institute of General Medicine, University of Lausanne, Switzerland.

GPs have to send index visit CRF to research team once a week, as well as end of follow up questionnaires (routine consultation 6 to 9 months after index visit or telephonic interview). Questionnaires for intermediate analysis at 3 months will be filled in by research team during a telephonic interview and kept in the research department.

A single code will be attributed to each patient and GP, so that complete anonymity is insured. Patients' details will be known only by their GP to insure maximal confidentiality. Each GP makes a ranking list of participating patients with name, code and phone number to assure the follow up. Furthermore, and only with patients' consent, mobile phone number is attached to identification code to allow the research team to contact patient in case of incomplete CRF. Mobile phone numbers will be deleted after intermediate analysis.

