### 3.1 Overall description

This trial aims to assess implementation of a new cardiovascular CPR in primary health care. It is built as a prospective cohort study of primary care patients with chest pain. The cluster randomized trial design allows us to randomize GP's offices in two groups, one using the CPR in daily practice and the other working without, according to usual care practice. Thus, randomization and intervention are targeted at the level of GP's offices. Patient's outcome however is measured at the individual's level thanks to a case report form (CRF). Use of the CPR is measured directly by a few questions intended for GPs.

GPs selected to use the cardiovascular CPR will get intensive training to make as sure as possible that they use it in an equivalent way (see Annex 1 for description of GPs training). GPs of the usual practice group should not be aware of the CPR and will not get any information about it. In both groups, GPs will have to fill in a CRF for each patient complaining of chest pain.

Follow-up ends nine months after patient's index visit. An intermediate analysis is planned at three months. Members of research staff are designed to make sure that case report forms are complete for each patient and will get in touch with every agreeing patient at three months (intermediate analysis). GPs will assure the follow up until nine months (end of follow up) either by telephonic interviews or usual consultation. The research staff will control the follow up and remember GPs if necessary.

Independent physicians will review a defined randomized number of cases. They will control patient's condition at the end of the follow-up, validate the correct management of patients and verify the validity of the initial diagnosis of cardiogenic chest pain.

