### **8.2 Monitoring of adverse events**

Intermediate analysis is done at 3 months after patients index visit to display any unexpected effect of the CPR. In case of unfavourable effect for patients included, study will be immediately stopped. For stopping rules, please refer to *Chapter 3.4*.

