## **9. Quality control and assurance**

### **9.1 Monitoring**

Follow-up will last 6 to 9 months, with intermediate analysis at 3 months. To insure the data collection and avoid loss of follow-up, a member of research team will phone patients at 3 months and will also contact GPs at 9 months to insure closing of the follow-up.

*Quality control* will be provided by an independent GP and a hospital internist not aware of the current study. They will both review 20% of the cases, randomly

selected, to insure correct management of patients and validity of the data collected before analysis. Both reviewing and follow up should certify as surely as possible and without any invasive procedure the correct diagnosis and management of patients' complaint.

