## Suivi à 3 et 9 mois

Questionnaire rempli par : infirmière de recherche (analyse intermédiaire à **3 mois**)   
 médecin (terme du suivi à **9 mois**)

No patient :	No médecin :	Date :
--------------	--------------	--------

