### **Diagnostic retenu pour la douleur thoracique :**

Maladie coronarienne : oui  / non

Degré de certitude : faible 0 - 1 - 2 - 3 - 4 fort

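### At 3 months a research nurse enters the CHD diagnosis and its certainty grade from a call to the patient, and nothing keeps the caller unaware of the arm

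*Protocol*

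**What the plan says.** Annex 3 is headed as a follow-up form for 3 and 9 months. Its first line, "Questionnaire rempli par : infirmière de recherche", assigns the 3-month completion to a research nurse and the 9-month completion to the physician. Its last block is "Diagnostic retenu pour la douleur thoracique", answered as CHD yes or no, followed by "Degré de certitude : faible 0 - 1 - 2 - 3 - 4 fort". Nothing on the form reserves that block for the physician.

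The source at 3 months is fixed in two places. Section 7.2: "Questionnaires for intermediate analysis at 3 months will be filled in by research team during a telephonic interview". Section 9.1: "a member of research team will phone patients at 3 months"; the GP is contacted only at 9 months. Section 6 also has the research team supply the impact and outcome criteria for the intermediate analysis.

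Section 3.1 gives one group of research staff two tasks: to "make sure that case report forms are complete for each patient and will get in touch with every agreeing patient at three months". The index-visit CRF (Annex 2) contains a score block and an appraisal block that only CPR-group physicians complete.

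The 3-month analysis carries the stopping rules of Section 3.4. Section 8.2 adds: "In case of unfavourable effect for patients included, study will be immediately stopped".

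**The concern.** A retained diagnosis and a grade of confidence in it are a physician's judgement. A patient on the telephone can say whether they were admitted, tested or sent to a specialist. They can give at best a second-hand account of what the GP concluded, and have no obvious basis for the GP's degree of certainty. The same field on the same form would therefore hold two different measurements, one at 3 months and another at 9.

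The second problem is knowledge of the arm. A caller who has checked the patient's CRF can see the arm from the completed CPR-only blocks and, in the CPR arm, the score. That knowledge can colour how any answer on the form is prompted and recorded, not only the CHD item.

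This matters because the 3-month analysis is the only planned look with stopping rules. Error unrelated to arm pulls a true difference towards zero; recording that depends on the arm can create a difference where there is none.

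**Working it through.** **The documents side by side**

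| Question | Text | Place |
|---|---|---|
| Who completes the form at 3 months? | Research nurse | Annex 3, first line |
| From what source? | Telephone interview with the patient | Sections 7.2 and 9.1 |
| Is CHD on that form? | Yes: CHD yes/no and certainty 0–4 | Annex 3, last block |
| Is GP confirmation routine at 3 months? | Not described; the GP or patient may be contacted where data are missing | Section 10.3 |
| Who sees the CRF? | The staff group that also makes the calls | Section 3.1 |
| Does the CRF show the arm? | Yes, through the CPR-only blocks | Annex 2 |
| Whose blinding is stated? | The person who randomises is blinded to GP identity, and the two reviewers are unaware of the study; nothing is said of callers | Sections 3.3 and 9.1 |
| Does independent review protect the interim? | No: it covers 20% of cases, at the end of follow-up | Sections 3.1 and 9.1 |

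The review covers 0.20 × 15,000 = 3,000 patients, and Section 3.1 places it at the end of follow-up, after the 3-month contact.

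**Link to stopping.** Sections 3.4 and 8.2 name no outcome. Section 6 lists two patient outcomes, hospitalisation and CHD, and Annex 3 collects both at 3 months. That an interim judgement on patients may draw on CHD is therefore an inference, though a reasonable one.

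**Illustrative size.** The plan gives no figure to reproduce. The CHD frequency of 12% is from Section 1.1. Sensitivity (Se) and specificity (Sp) of the nurse-recorded item are assumptions; the documents give neither.

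- Observed CHD = 0.12 × Se + 0.88 × (1 − Sp)
- Share of CHD-yes entries that are false = 0.88 × (1 − Sp) / observed CHD
- With the same error in both arms, observed difference = true difference × (Se + Sp − 1)

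| Se | Sp | Observed CHD | False share | Se + Sp − 1 | Shrinkage |
|---|---|---|---|---|---|
| 0.80 | 0.95 | 0.0960 + 0.0440 = 14.0% | 0.0440/0.1400 = 31% | 0.75 | 25% |
| 0.90 | 0.95 | 0.1080 + 0.0440 = 15.2% | 0.0440/0.1520 = 29% | 0.85 | 15% |
| 0.80 | 0.98 | 0.0960 + 0.0176 = 11.36% | 0.0176/0.1136 = 15% | 0.78 | 22% |
| 0.90 | 0.98 | 0.1080 + 0.0176 = 12.56% | 0.0176/0.1256 = 14% | 0.88 | 12% |

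Over the four corners the false share is 14–31% and the shrinkage 12–25%, before any effect of the caller knowing the arm.

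**The case against.** The case for leaving the plan alone has several parts.

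- **The endpoint is a physician's diagnosis.** Sections 3.2 and 6 place the CHD outcome at 9 months, when the physician completes the form. This stands. A reader might infer that the trial's CHD endpoint rests on a nurse's call; it does not.
- **No stopping rule mentions CHD.** This also stands. A reader might take CHD as a declared stopping trigger, but the text supports only that it is one of two listed patient outcomes available at that look.
- **A CHD difference is not a clear sign of harm.** The rule is an aid to diagnosis and does not cause CHD; missed disease could at first mean fewer CHD diagnoses in the CPR arm. This stands, and it argues for resting the interim patient-outcome comparison on hospitalisation. It does not make the nurse-recorded item more reliable.
- **Unblinding is not established.** Section 3.1 assigns both tasks to a group and does not say that the nurse calling a patient has read that patient's CRF. A reader might infer that callers know the arm. What the text shows is that exposure is likely and that nothing prevents it.
- **The nurse may not be guessing.** The protocol does not say how the certainty grade is to be obtained, and Section 10.3 allows contact with the GP when data are missing. That route is for gaps; an answer given by the patient leaves no gap to trigger it.
- **The accuracy figures are assumed.** They are, and they say nothing about this trial's actual error rate.

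**Conclusion.** The point holds for the 3-month analysis only. As written, a nurse records a CHD diagnosis and a certainty grade from the patient's account, without routine confirmation by the GP, and no step keeps the caller unaware of the arm. The only look with stopping rules can therefore draw on an unreliable CHD item and on answers collected by someone who may know the allocation. The ranges in the table show how large the dilution could be under the assumed accuracy; the documents support no firmer estimate, and no size can be put on bias from knowledge of the arm. This is a weakness worth correcting because correction is cheap. It does not invalidate the trial's 9-month results.

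**What to change.** 1. Split Annex 3. Remove the diagnosis and certainty block from the nurse's 3-month version and keep it on the physician's 9-month version.
2. Limit the 3-month call to what a patient can report: admissions, tests and specialist visits for chest pain. State that the interim comparison of patient outcome uses hospitalisation.
3. Give the caller the patient code and telephone number but not the CRF, and have another existing staff member check CRFs. Because the form header carries the GP number, the caller should not hold the list linking GP numbers to arms either.
4. If CHD status is still wanted at 3 months, take it from the GP and say in the protocol that it is a physician's diagnosis but not a blinded one: the GP knows the arm and, in the CPR arm, is asked to calculate the score. This cures the source problem, not the blinding.

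The cost of steps 1 to 3 is a second version of one form, a division of tasks and the loss of a CHD item at the interim. Step 4 keeps the item at the price of one extra GP entry per patient: 50 per GP, or up to 300 × 50 = 15,000 in all.
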